be provided with a copy of the consent form by the RC that can be emailed or mailed to the participant after consenting to participate. Once complete, the RC will reiterate the key aims and participant requirements (1 phone interview and the one adherence assessment), before giving the potential participant the opportunity to ask any questions they might have. The potential participant will be informed that they are free to withdraw at any time without penalty and all information will be provided to the subjects in terms that they can fully understand. There will be no exertion of any overt or covert coercion. Once the RC is satisfied that the potential participant understands the consent process and the nature of their participation in the research study, the potential participant will be asked to sign and date the online consent form. Participants will receive a signed consent form for their records by email. If an online consent cannot be obtained, we will proceed with a verbal consent. The consent date and name of the research coordinator that obtained the consent will be recorded in REDCap by the RC prior to starting the interview. Participants will receive a copy of the consent form for their records by mail or email depending on their preference.

If a patient is unable to complete an electronic consent due to inability to use technology for electronic consent, we request a waiver of documentation of informed consent and an alteration to obtain verbal HIPAA Authorization, since this study presents no more than minimal risk of harm to participants. For patients that are unable to complete electronic consent, research cannot practicably be conducted without the waiver or alteration. Obtaining written consent is not feasible since this clinic-randomized study will recruit patients from clinics all over the Chicagoland area (including North and West suburbs). In order to maintain the sample size necessary for meaningful data, we need to request a waiver of documentation of informed consent and alteration to obtain verbal HIPAA Authorization. Additionally, it is important that we do not exclude older adults solely based on inability to use technology, decreasing the diversity of the population. After verbal consent and HIPAA Authorization is obtained, the consent date and the name of the research coordinator that obtained the consent will be recorded in Redcap by the RC prior to starting the baseline interview.

NON-ENGLISH-SPEAKING PARTICIPANTS

Only English-speaking participants will be enrolled in this small pilot study.

WAIVER OR ALTERATION OF CONSENT PROCESS

We will obtain a partial HIPPA waiver for recruitment of patient participants in Aim 1 and Aim 2. For Aim 2, all participants will provide a signed HIPPA waiver so that we may report clinical outcomes described above in the measurement sections. We want to be sure we are contacting, screening, and enrolling participants for whom this research is tailored.

If a patient is unable to complete an electronic consent due to inability to use technology for electronic consent, we request a waiver of documentation of informed consent and an alteration to obtain verbal HIPAA Authorization, since this study presents no more than minimal risk of harm to participants. For patients that are unable to complete electronic consent, research cannot practicably be conducted without the waiver or alteration. Obtaining written consent is not feasible since this clinic-randomized study will recruit patients from clinics all

STU#: STU00217555

over the Chicagoland area (including North and West suburbs). In order to maintain the sample size necessary for meaningful data, we need to request a waiver of documentation of informed consent and alteration to obtain verbal HIPAA Authorization. Additionally, it is important that we do not exclude older adults solely based on inability to use technology, decreasing the diversity of the population. After verbal consent and HIPAA Authorization is obtained, the consent date and the name of the research coordinator that obtained the consent will be recorded in Redcap by the RC prior to starting the baseline interview.

PROTECTED HEALTH INFORMATION (PHI AND HIPAA)

We will obtain a partial HIPPA waiver for recruitment of patient participants in Aim 1 and Aim 2. We want to be sure we are contacting, screening, and enrolling participants for whom this research is tailored.

For Aim 2, all participants will provide a signed HIPPA waiver so that we may report clinical outcomes described above in the measurement sections.

QUALIFICATIONS TO CONDUCT RESEARCH AND RESOURCES AVAILABLE

The Center for Applied Health Research on Aging (CAHRA) directed by [name], MA, MPH, PhD, CAHRA serves as a research and education hub for geriatricians, gerontologists and aging health services researchers. This Center unites >70 faculty across clinical disciplines and from cognitive, behavioral, social and public health sciences throughout the university and the Northwestern Medicine health system. CAHRA's mission is to promote informed decision making and actions leading to optimal health and well-being among individuals and families over the life span.

Building off of [name] highly successful Health Literacy and Learning Program (HeLP), which was founded in 2004 to create a network of multidisciplinary faculty that could partner together to generate applied, innovative research that would help transform the delivery of healthcare for vulnerable patients (older adults are a specific target), CAHRA was launched in 2019 through an institution-created endowment and is now formally linked to IPHAM and the Department of Medicine. The Center is physically and strategically co-located on the same floor of the Arthur Rubloff Building as the Division of GIMG, as well as the Center for Behavioral Intervention Technologies (CBITs) and encompasses approximately 2,500 square feet of office space, in addition to dedicated research interview space.

The establishment of CAHRA demonstrates Northwestern's commitment to prioritizing aging research and to pursuing a leadership position in the field. The Center's six research programs are a reflection of the wide-ranging research portfolio of the Center's core faculty members: 1) Health Literacy & Learning, 2) Cognitive Aging, 3) Psychosocial Support, 4) Life Course Health, 5) Treatment Adherence, and 6) Measurement & Analysis. Together, CAHRA leads a robust research agenda to explore and understand the many factors that affect a person's ability to manage health throughout their life and use that knowledge to develop and disseminate interventions that support better health.

STU#: STU00217555

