We will adapt the already-built TAKE IT strategy for use in primary care, targeting older adults with MCC and polypharmacy (using Medicare Part D medication therapy management criteria of ≥ 8 medications). This intervention, renamed as the PATTERN study (**P**henotyping **A**dherence **T**hrough **T**echnology-**E**nabled **R**eports and **N**avigation) will be pilot tested at one or more Northwestern Medicine (**NM**) primary care practices to determine its acceptability, feasibility, and preliminary fidelity.

STUDY ENDPOINTS:

Regimen adherence utilizing a post-visit survey as measured by ARMS- D and/or ASK-12 is the **primary outcome** of interest.

Variable	Instrument(s) or Measure(s)	Source	Timing & Window		
			Screener	Post Visit Survey	6M
			Phone	Phone	
Outcome Measures					
Medication Adherence	ASK-12 and ARM-D	self-report		x	
Clinical outcomes	HbA1c	chart / EDW		x	x
	Cholesterol panel	chart / EDW		x	x
	systolic/diastolic blood pressure	chart / EDW		x	x
Acceptability	Qualitative	Theoretical Framework of Acceptability		x	

STU#: STU00217555

Secondary outcomes include clinical outcomes (e.g. A1c, blood pressure, cholesterol panel). Relationships between adherence and potential confounders (age, comorbidity, regimen complexity, internet use, dose of intervention, health literacy, patient activation, social support) will also be examined. Acceptability and fidelity/feasibility will also be examined. This may include examining how many participants in the intervention arm completed the adherence questionnaire and how many of those indicating an adherence challenge were responded to in some way by the clinic.

STUDY INTERVENTION

The goal of TAKE IT is to optimize adherence and to detect problems earlier to improve health outcomes in kidney transplant centers. TAKE IT includes the following intervention components that will be adapted and piloted for use in the PATTERN study for primary care among adults aged 65 and older with polypharmacy and multiple chronic conditions:

1. **An adherence assessment** that requests patients to report on their medication use, providing a link between the health center and patient beyond routine in-person visits. This assessment will identify patients at risk of non-adherence and categorize their adherence concern(s) as: cognitive, psychological, regimen, medical, social, economic.

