turn their video cameras off so only their audio is recorded. Specifically, the Northwestern research team will record the interview portions where participants are offering suggestions or giving us feedback on the adaptation of the TAKE IT intervention into the PATTERN study (as described above). We will not record any identifiable information (ex: medical records or responses to demographic questionnaires). Due to Zoom recording recommendations made by NUIT, interviews conducted with the Zoom software will be recorded to the Zoom Cloud. Recording to the Zoom Cloud, rather than directly to one's computer, prevents the recorded files from becoming corrupted and diminishing the quality of the recording (ex: failed recording where not everything is recorded).

The Zoom Cloud or Microsoft Teams recordings will be downloaded and saved onto secure FSM department servers. Only authorized research personnel will have access to the data. The recordings may be used solely by the Northwestern research team for analysis purposes only. Recordings from the qualitative research activities will be analyzed using a rapid approach to qualitative analysis. De-identified notes may be taken as needed. The recordings and notes will be stored on the FSM department servers for the duration of the study. At the conclusion of the study, all recordings will be destroyed.

If a participant is not willing to be audio recorded, then they will be unable to participate in the Aim 1 study activities. No pilot study activity will involve audio or visual recording; those activities will take place over the phone through a Northwestern phone line.

Aim 2: Pilot study (N=80; n=40 per arm)

For **Aim 2**, we will conduct a patient-randomized controlled trial at one Northwestern Medicine primary care practice and followed for 6 months. A total of 80 participants will be recruited and randomly assigned via REDCap once a primary care appointment is scheduled to either the PATTERN arm or usual care (N=80, n=40 per) arm. Usual care refers to the normal standard clinical practices at the participating practice(s).

Research activities (described in detail below) will include an adherence assessment (for those in the Pattern arm) and a post-visit survey (for both arms) which will be conducted over the phone via a Northwestern phone line.

Adherence assessments (part of the intervention)

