Participation in this study puts subjects at a minimal risk of discomfort or inconvenience, as they are primarily responsible for providing their own opinions and suggestions about intervention adaptation (Aim 1), or experiences with their prescribed medication taking behaviors (Aim 2). Nevertheless, some of the questions may be upsetting or make participants feel uncomfortable; participants may experience a sense of unease or shame while they complete measures of health literacy (Aim 2). Finally, participation may result in a loss of privacy, since research and oversight staff may review research findings.

POTENTIAL BENEFITS TO PARTICIPANTS

It is possible that subjects enrolled in the study may directly benefit from this study by having a better understanding of medication challenges and resources available for support. The results of this study may provide important information regarding how strategies can be implemented via available technology (e.g., the EHR) to phenotype and provide appropriate support to identified medication adherence challenges.

STU#: STU00217555

DATA MANAGEMENT AND CONFIDENTIALITY

The proposed pilot study uses a 1:1 randomized design that assigns patients to PATTERN or usual care. We will accrue 80 patients (to allow consenting to occur until we have 80 interviews), anticipating 90% retention for follow-up at about 2 to 4 weeks after primacy care visit, leaving a minimum 72 patients for primary analyses. High retention will be supported through close follow-up, and reminders.

As mentioned previously, regimen adherence during post-visit survey as measured by the ARMS-D and/or ASK-12 is the **primary outcome** of interest. **Secondary outcomes** include clinical outcomes (e.g. A1c, blood pressure, cholesterol panel). Relationships between adherence and potential confounders (e.g., age, comorbidity, regimen complexity, internet use, dose of intervention, health literacy, patient activation) may also be examined.

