As a small pilot study, appropriate bivariate analyses (chi square, t-test) will be performed to compare outcome by study arm. Exploratory analyses will apply generalized linear models (GLMs), adjusting for confounders, specifying the logit link function for binary outcomes and identity link for continuous outcomes. Treatment group will be the independent variable of primary interest, with usual care specified as reference group. We will also include baseline value of the outcome and any potential confounding covariates noted in bivariate analysis. For outcomes measured per medication as described in the **Measurement table** above, a generalized estimating equation (GEE) approach will be employed to adjust standard errors for within-patient correlation. Should PATTERN demonstrate a significant - or non-significant trend suggesting an effect on outcomes, **secondary analyses** will examine if any of the potential confounders considered exhibit any effect modification.

To understand the fidelity of PATTERN, we will determine the extent to which the intervention was implemented as planned to optimize it for a future multi-site trial. We will capture data from patient self-report and the EHR. Patients receiving PATTERN will be asked whether they received the EHR message and visited the portal. From the EHR, we will determine if the portal assessment was completed, the prevalence and type of patient-reported adherence concerns, whether the clinic read portal responses, and the average time from assessment submission to clinician or staff review, and/or response. We will examine if receipt and completion of EHR assessments and deployment of adherence support tools increases participant knowledge and medication taking behaviors.

Data Safety and Monitoring Board (DSMB). Because this is a small pilot, a formal DMSB is not required. However, we will identify two members of the Northwestern Pepper Center who will be given responsibility to review protocols, procedures, and concerns related to research integrity, including an approval of the methods and analysis plan. The DSMB will be organized by [name] and include an appropriate research biostatistician with related expertise. Meetings will take place via video/teleconference.

We will register the trial protocol at ClinicalTrials.gov.

STU#: STU00217555

Measures

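### Dose of intervention is listed as a potential confounder although it follows from randomisation; entered beside arm, it changes what the arm coefficient estimates

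*Protocol*

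**What the plan says.** The protocol names dose among the potential confounders twice. In Study Endpoints the list reads "potential confounders (age, comorbidity, regimen complexity, internet use, dose of intervention, health literacy, patient activation, social support", and there the relationships are to be examined as a firm intention. Under Data Management and Confidentiality the wording is softer: "Relationships between adherence and potential confounders (e.g., age, comorbidity, regimen complexity, internet use, dose of intervention, health literacy, patient activation) may also be examined".

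The analysis plan in the same section draws on potential confounders twice.

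- **Exploratory GLM.** "Treatment group will be the independent variable of primary interest, with usual care specified as reference group". On covariates: "We will also include baseline value of the outcome and any potential confounding covariates noted in bivariate analysis".
- **Secondary analyses.** The condition is "Should PATTERN demonstrate a significant - or non-significant trend suggesting an effect on outcomes". If it is met, these analyses "will examine if any of the potential confounders considered exhibit any effect modification".

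Neither step sets dose aside. The Aim 2 part of Procedures Involved describes the research activities as "an adherence assessment (for those in the Pattern arm) and a post-visit survey (for both arms" and defines usual care as the practice's normal standard of care. The fidelity paragraph of the analysis plan separately says: "We will examine if receipt and completion of EHR assessments and deployment of adherence support tools increases participant knowledge and medication taking behaviors".

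**The concern.** A confounder of a treatment comparison is a common cause of treatment and outcome. In a randomised trial, a variable that exists only because a patient was assigned to the intervention cannot be one. It lies downstream of assignment, on or near the path from arm to outcome. Listing it beside age and comorbidity invites the analyst to treat it as they are treated.

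The adjusted PATTERN estimate would then answer a different question from the unadjusted one: how patients in the PATTERN arm who received no dose compare with all of usual care. Those patients are self-selected. A reader would see an adjusted treatment effect that might appear to contradict the unadjusted comparison, in a pilot meant to inform a future multi-site trial.

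**Working it through.** **Inputs.** The protocol anticipates 90% retention of 80 patients: 80 × 0.90 = 72, which reproduces its stated minimum for primary analyses. With 1:1 allocation and equal loss that is n = 36 per arm. The protocol gives no effect size, SD or definition of dose, so effects below are in SD units and every uptake figure is an assumption. Dose is taken as zero in usual care. The models use least squares (identity link) with arm and dose only.

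**1. Effect modification by dose.** Arm is 0 in usual care and 1 in PATTERN, and dose is 0 in usual care, so arm × dose = dose for every patient. The columns (intercept, arm, dose, arm × dose) have rank 3 of 4 at every partial completion count tried, from 2/36 to 35/36, and also for a graded dose. The interaction cannot be separated from the dose slope. This is a property of the design matrix, so it holds under the logit link too.

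**2. What the arm coefficient becomes.** In a model with arm and dose, usual care fixes the intercept and PATTERN alone fixes the dose slope. Hence

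arm coefficient = (PATTERN mean − usual-care mean) − dose slope × m,

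where m is the mean dose in PATTERN. For a yes/no dose this is the mean of PATTERN non-completers minus the mean of usual care.

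**3. Loss of precision.** With s the SD of dose within PATTERN (divisor n), the variance is σ²[2/n + m²/(n s²)] against σ²(2/n) unadjusted. Therefore

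SE multiplier = √(1 + m²/(2s²)).

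For a yes/no dose with completion proportion p, m²/(2s²) = p/[2(1 − p)].

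| Completers of 36 | p/[2(1 − p)] | SE multiplier |
|---|---|---|
| 9 | 0.167 | 1.08 |
| 18 | 0.5 | 1.22 |
| 27 | 1.5 | 1.58 |
| 30 | 2.5 | 1.87 |
| 34 | 8.5 | 3.08 |
| 36 | – | not identified (rank 2 of 3) |

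Thirty of 36 corresponds to 83%, the TAKE IT completion figure in Background, which comes from another setting. Direct check: √(1/6 + 1/36) = 0.441 SD against √(2/36) = 0.236 SD, ratio 1.87.

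For an assumed graded dose scored 0/2/3 in 6/20/10 patients, m = 70/36 = 1.94 and s = 0.97, giving 1.73.

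**4. Shift in the estimate.** The size depends on the assumptions.

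- Total effect 0.5 SD, half of it through completion: the arm coefficient is 0.5 − 0.25 = 0.25 SD. Simulation of 4,000 trials gave 0.25 at 9, 18 and 30 completers.
- Benefit of 0.5 SD in completers only (5,000 simulated trials per scenario), with completion either unrelated to underlying adherence or correlated 0.5 with it on the latent scale:

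| Uptake | Randomised contrast | Arm given dose, unrelated | Arm given dose, related |
|---|---|---|---|
| 50% | 0.250 | 0.004 | −0.399 |
| 83% | 0.415 | −0.002 | −0.746 |
| 95% | 0.475 | 0.000 | −1.018 |

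With dose left out, the simulated arm coefficient at 83% was 0.414 and 0.416, close to the true 0.415.

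**5. Would dose be selected?** The protocol does not define its bivariate screen. If the screen were association with arm, two-sided Fisher tests against 0/36 give p = 0.24 at 3/36, 0.054 at 5/36, 0.025 at 6/36 and 0.002 at 9/36. At the 0.05 level dose would enter from 6/36 (17%) upward. If the screen were association with the outcome, dose was selected in 54% (unrelated) to 89% (related) of the step 4 simulations at 83% uptake.

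**The case against.** The strongest reply is that the harmful model is inferred. The sentences listing dose speak of relationships with adherence, which for dose reads naturally as a dose-response question, and the fidelity paragraph plans much the same. The GLM sentence names no covariates and no screening criterion, and the final covariate set is commonly left to an analysis plan, which a biostatistician is to help review. It can also be said that:

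- the aliased interaction exposes itself, because software drops or flags it;
- the magnitudes rest on an undefined dose and on uptake borrowed from kidney transplant recipients doing monthly assessments, whereas this trial has one assessment;
- the models concerned are exploratory, in a pilot whose aim is feasibility and acceptability.

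Much of this stands as a limit on scope. Entry of dose is permitted, not prescribed. The sizes are illustrations, and the standard-error and simulation figures do not cover the logit models. The main comparison is untouched. What does not stand is treating the matter as a detail left for later. The protocol itself puts a post-randomisation variable in the wrong class, in two places, and its two rules for that class contain no exemption. Software would reveal the redundant interaction, but it would not flag dose entered beside arm at partial completion.

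A further objection concerns the remedy. The Measures section gives no time point for internet use, patient activation or social support, and the consent section tells participants of one phone interview. If these items are collected only after the visit, limiting adjustment to covariates fixed before randomisation may exclude some of them. That is a real but small cost, and the exclusion is proper: a covariate that the intervention could have changed should not be adjusted for.

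**Conclusion.** The concern holds. Dose of intervention is a consequence of assignment, not a potential confounder of the randomised comparison. Two results follow for any coding that is zero in usual care: effect modification by dose cannot be estimated apart from the dose slope, and an arm coefficient adjusted for dose is the effect at dose zero. That zero is inferred from the delivery of assessments to the PATTERN arm only.

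The size is uncertain. With 36 per arm and a yes/no dose, the SE multiplier runs from 1.08 at 25% completion to 1.87 at 30 of 36, and the arm effect is not identified at full completion. The shift in the estimate depends on how much of the effect acts through dose and on whether completers differ from non-completers.

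The damage is confined to the exploratory GLMs and the conditional effect-modification analyses, and arises only if dose is selected. The unadjusted chi-square and t-test comparisons by arm are unaffected. It should be corrected, but it does not threaten the main comparison.

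**What to change.** 1. Delete dose of intervention from the potential-confounder lists in Study Endpoints and in Data Management and Confidentiality. This also removes it from the adjustment and effect-modification sets.
2. Analyse dose only within the PATTERN arm, under the fidelity analysis already planned for receipt and completion of assessments, and label the result as a non-randomised comparison.
3. In the sentence "We will also include baseline value of the outcome and any potential confounding covariates noted in bivariate analysis", insert the words *fixed before randomisation and* after the word covariates, so that only such variables can enter the model.

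The cost is wording only, with no new data collection. The small downside is that the exploratory models may have fewer covariates if some characteristics are recorded only at the post-visit interview and could have been altered by the intervention. Age and other characteristics that assignment cannot change remain eligible whenever they are recorded.
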